### **Enhancement Study**

We used a quasi-experimental design to compare rDirectCAM with DirectCAM. Our hypothesis posits that the observed difference in outcome effects between rDirectCAM and DirectCAM is less than a predetermined non-inferiority margin ( $-\Delta$ ). These margins were selected based on the MCID or minimal detectable change (MCD) of the studied outcomes among MS population published in literature (MFIS= 4, BBS= 3, TUG= 10.6, FTSTS= 13, Grip-strength= 10.5, SF-36 Physical functioning= 7.1 and SF-36 pain= 4.9).

Specifically, we hypothesized that the effect of rDirectCAM was not inferior to that of DirectCAM by a margin that was considered clinically acceptable, thereby affirming the non-inferiority of rDirectCAM in comparison to DirectCAM. In other words, if the resulting *p*-value was significant, this would mean that we rejected the null hypothesis which stated that the difference in the effect between two arms were more than the non-inferiority margin. Statistical significance level of 0.05 and at confidence interval 95%, same as superiority trials,

was applied to determine non-inferiority. To achieve a balance between the study arms, several analyses involved regression-based parametric adjustment measures that are sensitive to model misspecification. Propensity scores are another widely used measure to achieve balance or matching between the study arms. These scores model the probability of being assigned to the given treatment conditional on observed baseline covariates obtained via measures including matching, inverse probability treatment weighting (IPTW), and stratification and covariate adjustment. Matching-based measures such as nearest neighbor matching algorithm often led to study participants being excluded when a match was not available. This may have potentially biased the effect estimates. When this occurred, we utilized stabilized IPTW, a non-parametric balancing strategy, to achieve balance between the two study arms (rDirectCAM and DirectCAM). Using this weighted analysis, we modeled the causal parameter as the inverse of the conditional probability of receiving the treatment given the observed covariates, a technique that provides asymptotically unbiased estimates and uses data on all available study participants across the two arms.

Our general analytic approach was to leverage the linear mixed modeling framework to account for repeated nature of data. Appropriate contrasts were applied using the fitted model. Sensitivity analyses were performed to assess distributional and other modeling assumptions. Missing data was imputed using multiple imputation where necessary. The non-inferiority ( $-\Delta$ ) of the rDirectCAM was assessed by comparing the lower limit of confidence interval for each outcome to its corresponding margin so that if the lower bound was above this margin, then the rDirectCAM was deemed non-inferior. For the MFIS and TUG assessments, wherein an elevated score signified a deterioration in the outcome, we juxtaposed the upper limit of the

confidence interval against a predefined margin. Non-inferiority was deemed established when the upper bound was less than  $-\Delta^{133}$ .

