*Berg Balance Scale (BBS).* The BBS is administered by a single rater who scores an individual's balance performance from a value of 0 (cannot perform) to 4 (normal performance) on a total of 14 tasks. Tasks incorporate several activities related to static balance such as sitting to standing, retrieving an object from the floor, standing with eyes closed, and standing on one foot. The test was administered with a ruler, two chairs (height: 45–47 cm; one with armrests and one without), a footstool, a 15-foot walkway, and a stopwatch. Previous research has reported a minimum detectable change of seven points in multiple sclerosis.

*Five Time Sit To Stand (FTSTS).* The FTSTS was used to assess balance, it measures the amount of time it takes for an patient to transfer from a seated position to standing position and back to sitting five times. The FTSTS test has been shown to effectively assess lower extremity strength in individuals with MS. Furthermore, its reliability and validity have been established in various other neurological disorders such as stroke and Parkinson's disease.

*Six Minute Walk Test (6MWT).* The 6MWT was used to assess walking endurance, in which total distance traveled over 6-minute period was recorded in meters. The test was administered in a hallway with an unobstructed 50-foot path marked with two cones. Perception of fatigue was measured and recorded with the BORG Rating of Perceived Exertion (RPE) before and after the test. The test has been reported to have excellent test-retest (ICC = 0.97) in the stroke population and people with MS and has known validity for use in measuring endurance in persons with MS.

*Timed Up and Go (TUG).* The TUG test was used to assess mobility and balance, which involves recording the time required to rise from a chair, walk to a 3-meter mark, turn around, walk back to the chair, and sit down. The test is a valid test of mobility, balance, and walking ability in people with MS, with excellent test-retest reliability (ICC = 0.96).

*Grip Strength Hand Dynamometer.* Hand grip strength was measured using a hand dynamometer with the dominant and non-dominant hands. The mean of three trials for each hand was used as the actual score. The test was conducted with the participant sitting in a chair, shoulder adducted and neutrally rotated, elbow by their side and flexed

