The estimated changes between groups and within groups were then compared to minimally clinically important difference (MCID) published in literature for the studied outcomes among people with MS. For primary outcomes, the published MCID was for MFIS= 4 and SF-36 pain score = 4.9. For secondary outcomes, MCID for 6MWT= 21.56, BBS= 3, TUG= 10.6, FTSTS= 13 and grip strength= 10.5. For exploratory outcomes, MCID was published for SF-36 physical functioning (MCID= 7.1).

Aim 2 was about evaluating pre-specified confirmatory HTE analyses by testing the role of 4 prespecified moderators (age, geographic location/residence based on participants zip codes, type of MS and severity of MS) on each of the primary self-reported outcomes: MFIS, SF-36 MCS, SF-36 PCS, SF-36 pain domain scale, and GLTEQ. We had 4 families of hypothesis tests within this aim – one for every moderator with 2 levels (PDDS 0-3 [without assistive devices] and PDDS 4-7 [with assistive devices]). Our model was like the one used in the primary aim except that we augmented the model with an additional two-way interaction term between moderator (e.g., education level) and Arm (moderator X Arm), and a 3-way interaction term between moderator x Arm x Time. When a 3-way interaction was observed, post-hoc tests were performed to determine the differential influence of the moderator to one treatment versus another, controlling for family-wise error utilizing the Holm-Bonferroni method. We expected no greater than 11 post-hoc tests per pre-specified moderator and used contrast statements to achieve this. Our missing data strategy was similar to that in the primary aim.

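### The TUG, FTSTS and grip non-inferiority margins lack units, a settled source type and clinical justification; if TUG is in seconds, a positive TUG verdict would be weak evidence

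*Combined protocol and SAP*

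**What the plan says.** The Enhancement Study part of Analytical and Statistical Approaches sets the standard: rDirectCAM is to be shown "not inferior to that of DirectCAM by a margin that was considered clinically acceptable". On where the margins come from it says: "These margins were selected based on the MCID or minimal detectable change (MCD) of the studied outcomes among MS population published in literature". Seven values follow, among them TUG 10.6, FTSTS 13 and "Grip-strength= 10.5". None of these three has a unit, and no outcome is assigned to one source or the other.

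The Main Study part of the same chapter lists the same seven values as MCIDs. The sentence on secondary outcomes opens "For secondary outcomes, MCID for 6MWT= 21.56" and runs on to "TUG= 10.6, FTSTS= 13" and grip strength 10.5.

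For the Berg Balance Scale (BBS), Study Outcomes cites a "minimum detectable change of seven points in multiple sclerosis", while the BBS margin is 3.

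The decision rule closes the Enhancement Study analysis text. The lower confidence limit is compared with the margin, except for MFIS and TUG, where higher is worse and the upper limit must lie below −Δ.

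**The concern.** A minimal detectable change describes how far one person's score must move to exceed measurement error. It does not say how much loss in a group mean would be clinically acceptable, which is the standard the plan sets for itself. The plan admits detectable change as a source, labels the same numbers MCID elsewhere, and argues the clinical acceptability of none of the three values at issue. The BBS figures show that the two kinds of threshold can differ more than twofold (7 against 3), so the label matters.

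A margin that is wide relative to the test lets a materially worse arm pass. What is at stake is a published statement that remote delivery is non-inferior for mobility and strength, resting on margins that a reader cannot interpret.

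**Working it through.** **1. The plan's own figure.** Sample Size Calculations gives 55 rDirectCAM completers and 74 enrolled at 25% attrition: 55 / 0.75 = 73.3, rounded up to 74. This reproduces. The 55 cannot be checked, because the plan gives neither an MFIS SD nor the number of DirectCAM comparators. Only the MFIS margin of 4 entered this calculation; the TUG, FTSTS and grip margins did not.

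**2. Scale of the TUG margin.** Inputs from the plan:
- TUG is timed over 3 m out and 3 m back, so 6 m (Study Outcomes).
- The 25-foot-walk (T25FW) cut-points between TEAMS levels are 6 s and 8 s (Interventions). 25 ft = 7.62 m.
- In the Enhancement study only participants with PDDS 0-4 take TUG.

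Time to walk 6 m = (6 / 7.62) × T25FW:
- at 6 s: 4.7 s, and 10.6 / 4.7 = 2.2
- at 8 s: 6.3 s, and 10.6 / 6.3 = 1.7

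Rising, turning and sitting are excluded. The margin equals the walking time only when T25FW = 10.6 × 7.62 / 6 = 13.5 s. All of this takes 10.6 to be in seconds. That is the natural reading for a timed test whose confidence limit is compared directly with the margin, but the plan does not state it.

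**3. Chance that a worse arm passes on TUG.** Assumptions, none given in the plan:
- true worsening of 5 s
- SD of change from 2 to 15 s
- two-sided 95% CI, with the margin read as +10.6 in the harmful direction
- 55 v 266 completers, where 266 is half of the 533 planned Main Study completers

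SE = SD × √(1/n₁ + 1/n₂), and P(pass) = Φ((10.6 − 5)/SE − 1.96).

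| n₁ v n₂ | SD (s) | SE | (5.6/SE) − 1.96 | P(pass) |
|---|---|---|---|---|
| 55 v 266 | 2 | 0.30 | 16.9 | >99.9% |
| 55 v 266 | 8 | 1.19 | 2.77 | 99.7% |
| 55 v 266 | 15 | 2.22 | 0.56 | 71% |
| 30 v 30 | 8 | 2.07 | 0.75 | 77% |

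The 30 v 30 row allows for fewer TUG-eligible participants. The sample-size section uses a one-sided 0.05 test, whereas the analysis section uses a 95% CI. With 1.645 in place of 1.96, every probability would be higher.

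**4. Comparison with MFIS.** Back-solving the plan's own power statement (margin 4, one-sided 0.05, 80% power, ANCOVA with r = 0.7):
- largest SE = 4 / (1.645 + 0.842) = 1.609
- implied SD = 1.609 / (√(1 − 0.7²) × √(1/55 + 1/n₂)), which is 11.8 with n₂ = 55 and 15.2 with n₂ = 266
- margin / SD = 4 / 11.8 = 0.34 and 4 / 15.2 = 0.26

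For 10.6 to be as strict, the TUG SD would have to be 10.6 × 11.8 / 4 = 31 or 10.6 × 15.2 / 4 = 40. In seconds, that is several times the walking times in step 2.

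**5. FTSTS and grip.** The plan offers no expected value, SD or companion measure from which to judge 13 or 10.5, so no equivalent check can be made.

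**6. The written decision rule.** Take the difference as rDirectCAM minus DirectCAM. For an outcome where higher is worse, the stated hypothesis corresponds to an upper limit below +Δ. The text says below −Δ. With no true difference, SD 8 and 55 v 266, that literal rule passes with probability Φ(−10.6/1.19 − 1.96), which is effectively zero. FTSTS is also timed, but it is not named with MFIS and TUG. It therefore falls under the lower-limit rule, which a slower rDirectCAM arm could meet.

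**The case against.** A reader might infer that the three margins are minimal detectable changes. The documents do not show that. The Enhancement section offers either source, the Main Study section says MCID, and only the cited sources could settle it. The BBS example partly favours the plan: where both kinds of value appear, the smaller one became the margin.

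A reader might also infer that the margins are too wide ever to fail. That is not supported either. A true TUG worsening near or above 10.6 would fail, and the SDs and comparator number above are assumed. Propensity weighting could also reduce the effective sample size. At SD 15, or with small groups, a 5 s worsening fails a quarter of the time or more. If 10.6 is a percentage, the scale check does not apply.

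The walking-time comparison has limits too. Level 3 has no upper T25FW bound, PDDS 4 is grouped with users of assistive devices, and T25FW is walked as fast as is safe whereas the TUG description gives no such instruction. Some participants will therefore have longer TUG times than the cut-points suggest. Finally, the literal −Δ rule makes TUG nearly impossible to pass.

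These points narrow the concern without removing it. The absent units, unreconciled labels and missing clinical argument are facts of the text. The −Δ rule conflicts with the plan's own hypothesis and cannot justify the margin.

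**Conclusion.** The concern holds in a limited form. The plan promises clinically acceptable margins, admits a source that does not provide them, does not say where it used that source, and gives TUG, FTSTS and grip no unit and no justification. For TUG in seconds with the +Δ reading, the margin is 1.7 to 2.2 times the walking time at the cut-points. A true 5 s worsening would be called non-inferior at least 99.7% of the time with 55 v 266 and an SD of 8 s or less. That SD already exceeds the walking times in step 2. A positive TUG verdict would be weak evidence unless SDs are very large.

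FTSTS and grip raise the same question of principle, but no magnitude can be given. The documents do not support a claim that non-inferiority is guaranteed on any of the three, nor that these values are known to be detectable changes. All three outcomes are secondary, and the MFIS margin that sized the study is not affected by the missing units or source type.

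**What to change.** - State the unit and source type (MCID or detectable change) of every margin, and reconcile the Main Study and Enhancement Study sections.
- For any of TUG, FTSTS and grip whose margin is a detectable-change value, or is not justified as a clinically acceptable difference between group means, report the adjusted difference with its 95% CI and make no non-inferiority claim.
- Correct the decision rule so that its sign matches the stated hypothesis for outcomes where higher is worse, and include FTSTS among them. Reconcile the one-sided 0.05 in the sample-size section with the 95% CI in the analysis section.

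This changes wording only; no new data are needed and the estimates stay the same. The cost is that up to three secondary outcomes may carry no formal non-inferiority statement.

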## Sample Size Calculations and Study Power

For the Main study an *a priori* power analysis was conducted based on sample size estimation for longitudinal designs with attrition with at least 30 sites. Based on the conservative power and sample size calculations, the project was powered for a minimum of 533 participants completing the study with an assumption of a 35% attrition rate; therefore, a total estimated sample size of 820 was needed to detect a between group effect. We assumed intent to treat analyses, 80% power, two-sided family-wise error rate of 0.05, intra-class correlation of 0.05, and a correlation of 0.3 among repeated measures. We also assumed an attrition rate of 35% and a small minimally detectable effect size of 0.2. We make a conservative assumption that the correlation between repeated measures would be 0.3. We have four primary and four secondary outcomes and hence the sample size was estimated after accounting for multiple testing and with a type 1 error rate of 0.00625 for each hypothesis test.

[figure not shown]
For the Enhancement study, we assumed ANCOVA with a pre-post correlation of 0.7, 80% power, one-sided test with statistical significance of 0.05, and attrition rate of 25%. Further, these sample size calculations assumed a non-inferiority margin of -4 units for MFIS, where fatigue is one our key primary outcome identified by the stakeholders in our project. A change of 4 or greater has been found clinically meaningful for quality of life. Based on these assumptions a sample size of 55 completers in rDirectCAM were needed and with an attrition

rate of 25%, we needed 74 participants in rDirectCAM.

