## Analytical and Statistical Approaches

### **Main Study**

Our analysis was following ITT protocol as all participants assigned to the randomized clinics and completed baseline assessment were included in the analysis.

Our primary hypotheses were about comparing the change in the 11 outcomes (listed in **Table 4**) between baseline and 12th month follow-up across the two arms. We considered these 11 hypothesis tests for the 11 outcome variables as part of a single family of hypotheses. We employed the Holm-Bonferroni method for controlling the overall family wise error rate and computed adjusted *p*-values. For each outcome we used a linear mixed effects model, with TeleCAM arm as the reference category, and accounting for the correlated nature of the data due to the nesting of participants within a clinic as random effects. Crude models included fixed effects included both Arms (TeleCAM, DirectCAM), Time (baseline [reference], 3 month, 6 month, 12 month), an Arms X Time interaction, and accounted for randomization strata (clinic location being urban vs. non-urban). The interaction of Arms and Time variables was the primary effect of interest since it quantified the differences within Arm change in the outcome from baseline over time of the two Arms. For example, based on the fitted model that included the interaction between Arm and Time, the difference in change over time from baseline to 12 months between DirectCAM and TeleCAM were estimated. Contrast statements were used to test the null hypotheses in conjunction with the fitted model coefficients and standardized differences in the average treatment effect reported. The estimates of the change in health and function outcomes for each arm and their 95% confidence interval were also reported. As a sensitivity analysis, similar models additionally adjusted for sex, race, and post-COVID data collection measure indicated were also ran. Note that, since post-COVID, data collection for patient reported outcomes was conducted remotely for remaining participants, the former was also included as a covariate in the adjusted model. Next, missingness in primary and secondary outcomes were addressed using multiple imputation technique (MCMC) via PROC MI in SAS,

assuming missing at random. Additional sensitivity analyses were conducted using wild bootstrap to assess the robustness to model assumptions.

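### The Enhancement study gives seven outcomes their own non-inferiority verdict at an unadjusted level, although it was sized for one MFIS test

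*Combined protocol and SAP*

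**What the plan says.** **Decision rule.** Under Analytical and Statistical Approaches, Enhancement Study, margins are listed for seven outcomes: MFIS 4, BBS 3, TUG 10.6, FTSTS 13, grip strength 10.5, SF-36 physical functioning 7.1 and SF-36 pain 4.9. The level is "Statistical significance level of 0.05 and at confidence interval 95%, same as superiority trials". Non-inferiority is decided by "comparing the lower limit of confidence interval for each outcome to its corresponding margin", with the upper limit used instead for MFIS and TUG. When a limit clears its margin, rDirectCAM is declared non-inferior. Nothing in the section combines or ranks the seven results.

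**Sizing.** Sample Size Calculations and Study Power says that "these sample size calculations assumed a non-inferiority margin of -4 units for MFIS". The other inputs are "we assumed ANCOVA with a pre-post correlation of 0.7, 80% power" and a "one-sided test with statistical significance of 0.05, and attrition rate of 25" percent. The result is 55 rDirectCAM completers and 74 enrolled. Fatigue is described there as one key primary outcome, not as the only confirmatory one.

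**Main study.** For the comparison of the randomized arms the plan puts 11 outcomes in one family: "We employed the Holm-Bonferroni method". Holm-Bonferroni is used again for the moderator post-hoc tests. It is not mentioned for the Enhancement study, and the Research Analysis Changes do not add it.

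**Visits.** Table 5 shows rDirectCAM follow-up at months 3 and 6. The Enhancement analysis does not say which visit carries the verdict.

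**The concern.** The rule is applied outcome by outcome, but its conclusion is worded about the treatment. As written, a pass on any of seven outcomes can be presented as rDirectCAM being non-inferior. No stated rule limits the error rate of that broader statement.

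Two features make this an inconsistency within the plan rather than a matter of taste. The number of completers was derived for one test of one outcome, whereas the analysis issues seven verdicts. And the plan treats 11 outcomes in the Main study as a family that needs control, but leaves the Enhancement outcomes uncontrolled. SF-36 physical functioning is only exploratory in the Main study, yet here it gets a verdict at the same level as MFIS. TUG and BBS are not done in participants with PDDS 5 to 7, so their verdicts rest on only part of an arm that was sized for MFIS.

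**Working it through.** **Inputs from the documents.** Seven outcomes with margins; level 0.05 with a 95% interval (Enhancement analysis); one-sided 0.05, power 80%, pre-post correlation 0.7, MFIS margin 4, 55 completers, 25% attrition (sample size section).

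**Inputs not in the documents.** The MFIS standard deviation, the number of DirectCAM comparators and the correlations among outcomes. Ranges are shown for these.

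**1. The plan's own figure.** 55 / (1 − 0.25) = 73.3, rounded up to 74, which matches. The 55 cannot be reproduced without the SD and the comparator number. Solving backwards with a true difference of zero:

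SD = 4 / [(1.645 + 0.842) × √(1 − 0.7²) × √(1/55 + 1/n_C)]

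This gives an SD of 11.8 with 55 comparators, 15.2 with 266 and 15.7 with 410.

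**2. The per-test level.** One bound of a two-sided 95% interval is a one-sided test at 0.025. The sizing uses one-sided 0.05. The text does not settle which applies, so both are carried forward.

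**3. Chance of at least one false verdict.** Each test is taken as one-sided against its own margin, with all seven true differences at their margins. Under independence it is 1 − (1 − α)^7:

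- α = 0.025: 1 − 0.975^7 = 16.2%
- α = 0.05: 1 − 0.95^7 = 30.2%

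With equally correlated normal test statistics (simulation, 1,000,000 draws):

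| Correlation | α = 0.025 | α = 0.05 |
|---|---|---|
| 0 (formula) | 16.2% | 30.2% |
| 0.3 | 13.7% | 24.5% |
| 0.5 | 11.5% | 20.3% |
| 0.7 | 8.9% | 15.8% |

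**4. What correction would cost MFIS.** If 55 gives 80% power at one-sided 0.05, the margin lies 1.645 + 0.842 = 2.486 standard errors from zero (unrounded inputs). Power at another level is Φ(2.486 − z), whatever the SD:

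- One-sided 0.025 (z = 1.960): 70.1%
- 0.05/7 = 0.00714 (z = 2.450): 51.5%
- 0.025/7 = 0.00357 (z = 2.690): 41.9%

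The last two are for the first Holm step, so they are lower bounds on MFIS power within a seven-outcome Holm family. Keeping 80% at that step multiplies the sample size by 1.75 or 2.02. At a fixed comparator ratio, 55 completers become 97 (130 enrolled) or 111 (148 enrolled). These are scalings of the plan's 55, not independent calculations.

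**5. Splitting into two ungated families.** MFIS at full α plus a separate Holm family on the other six, with no gate between them, gives about 1 − (1 − α)² if the two are independent: 9.75% at 0.05 and 4.9% at 0.025. Both are about twice the nominal level.

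**The case against.** The strongest reply is that no text says one pass among seven establishes overall non-inferiority. If seven outcome-specific conclusions are reported separately, each keeps its own error rate, and in a quasi-experimental add-on the need to adjust is partly a matter of judgement. If all seven had to pass, or if MFIS were the only confirmatory test, no correction would be needed. This is fair, but neither of those rules is written, and the verdict is worded about rDirectCAM as a whole. Sizing on MFIS does not by itself restrict the decision rule to MFIS.

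Three stronger readings are tempting but not supported:

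- **That the plan controls family-wise error for every Main outcome.** It does so for 11. The exploratory outcomes lie outside that family, and the mediation analyses of secondary and exploratory outcomes carry no stated correction.
- **That 30% is the figure.** The decision rule uses a 95% interval. Read as two-sided, that makes 16% the independent figure; one-sided 0.05 appears only in the sizing.
- **That both visits are tested.** Fourteen independent tests would give 29.8% or 51.2%, but no text says both visits carry a verdict, and ANCOVA with a single pre-post correlation suggests one post-baseline comparison. The supportable criticism is that the visit is not named.

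**Conclusion.** The point holds as a gap in specification. Seven verdicts are issued at an unadjusted level in a study sized for one, without the control that the plan uses for the Main study's 11 outcomes.

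The size is a worst case, because it requires all seven true differences to sit at their margins together. It also depends on which level is meant and on correlations that the documents do not give. Within the range shown, the chance of at least one false verdict is above 5% at either level. A reader might infer that the error rate of any Enhancement conclusion is far above 5%. The documents do not support that: each single-outcome statement keeps its own level, and the inflation concerns a claim about rDirectCAM drawn from whichever outcomes pass.

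The unsettled level matters even for MFIS alone. Using the two-sided 95% bound in place of the planned one-sided 0.05 lowers its power from 80% to 70.1%.

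**What to change.** 1. State one level for the non-inferiority test and make the sample size and analysis sections agree on it.
2. Make MFIS at one stated visit the single confirmatory non-inferiority test. This keeps the one-test basis of the 55 completers. The study closed on November 1, 2021, so the choice of outcome and visit must be disclosed as post hoc unless an earlier record supports it.
3. Report the other six outcomes as estimates with intervals and no non-inferiority verdict, or test them under Holm only if MFIS passes. An ungated second family would about double the error.
4. Alternatively, put all seven in one Holm family and accept that MFIS power at the first step falls to 51.5% or 41.9%, depending on the level.

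The change needs wording and relabelling of results, and no new data. The downside is weaker claims for six outcomes that the study was not sized for.

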## Time Frame for the Study

For the Main study, TEAMS launched its participant recruitment in October 2017 and ended participant enrollment in 2019. **Figure 4** shows the timeline for a few of the major milestones completed during the study period. Recruitment for the rDirectCAM group (Enhancement study) was not necessary as we had interested participants who already signed up the study via our website or through our clinic partners but were not able to enroll before the Main study needing to be ceased due to the pandemic. We established a protocol for conducting the teleassessments and tele-training and developed a structured set of procedures for equipment purchase and shipping/scheduling based on the Enhancement supplement received in May 2020. We began participant screening for the Enhancement study on September 10, 2020, with 100% enrollment completed on March 22, 2021. The study was closed on November 1, 2021.

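### rDirectCAM is compared with DirectCAM participants from an earlier, non-overlapping enrolment period, and weighting on baseline covariates cannot secure the unbiasedness that the plan states without conditions

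*Combined protocol and SAP*

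**What the plan says.** The Enhancement Study part of Analytical and Statistical Approaches is open about the lack of randomisation: "We used a quasi-experimental design to compare rDirectCAM with DirectCAM". It seeks balance through propensity scores: "These scores model the probability of being assigned to the given treatment conditional on observed baseline covariates". Where matching would drop participants, stabilised inverse probability of treatment weighting (IPTW) is used instead and is described as "a technique that provides asymptotically unbiased estimates and uses data on all available study participants across the two arms". The weights are said to depend on the observed covariates, but no assumption is attached to the unbiasedness. That section does not list the propensity covariates, and Potential covariates names no calendar variable. On robustness it says: "Sensitivity analyses were performed to assess distributional and other modeling assumptions".

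Time Frame for the Study gives the dates. For the Main study, "TEAMS launched its participant recruitment in October 2017 and ended participant enrollment in 2019". For rDirectCAM, "We began participant screening for the Enhancement study on September 10, 2020, with 100% enrollment completed on March 22, 2021". The rDirectCAM participants were "interested participants who already signed up the study via our website or through our clinic partners but were not able to enroll" before the pandemic stopped the Main study.

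Study Outcomes and Table 5 place DirectCAM assessments at the clinic and rDirectCAM assessments on a video platform. There is an exception late in the Main study: "post-COVID, data collection for patient reported outcomes was conducted remotely for remaining participants". A covariate for this enters the Main-study adjusted model only. The March 24, 2020 entry under Changes to the Original Study Protocol adds that 25 DirectCAM participants who had begun the intervention were offered remote delivery.

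**The concern.** IPTW removes confounding by the variables in the propensity model, and only where both arms contain people at each level of those variables. Enrolment date meets neither requirement: it is not named as a covariate, and no DirectCAM participant enrolled in the rDirectCAM window. Whatever changed fatigue, pain or function between baseline and follow-up in 2020-2021, but not in the earlier years, is therefore read as an effect of remote delivery. Assessment mode has nearly the same structure.

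The Enhancement study's central question is at stake. A period or mode effect that improves the change in rDirectCAM leads to non-inferiority being declared too often. One that worsens it makes a programme that is truly non-inferior fail. Nothing in the planned analysis would show which had happened, and the stated unbiasedness tells the reader that neither can happen in large samples.

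**Working it through.** **Overlap in time.** If DirectCAM enrolment ended on the last day of 2019, the gap to 10 September 2020 is 254 days. If it ran until the March 24, 2020 entry that suspended on-site visits, the gap is still 170 days. The shared follow-up visits do not overlap either. The latest DirectCAM 6-month visit falls at about the end of June 2020 (about September 2020 on the wider reading), and the earliest rDirectCAM 3-month visit at about December 2020. The probability of being in rDirectCAM given enrolment date is thus 0 or 1, and positivity fails for period.

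**Season.** October 2017 to 2019 includes every calendar month, so it includes the September-March months of rDirectCAM. Season is unbalanced, but it overlaps and can be modelled.

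**Does weighting remove a period shift?** A simulation used 2,670 DirectCAM and 550 rDirectCAM participants (large numbers, to show asymptotic behaviour) and 300 replicates. It had two measured confounders, a true delivery effect of 0, and a shift of b points in favour of the later arm. With b = 0, the unadjusted bias was 1.19 and the IPTW bias 0.01. With b = 1, 2 and 4, the IPTW estimate was -0.99, -2.02 and -4.00. Weighting removed the measured confounding and left the shift intact.

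**The plan's own sample size.** Sample Size Calculations and Study Power gives 55 completers and 25% attrition: 55/(1 - 0.25) = 73.3, rounded up to 74, which matches. The 55 cannot be checked, because no MFIS standard deviation and no allocation ratio are given. With the stated correlation of 0.7, one-sided 0.05 and 80% power, 55 follows at 1:1 if the raw SD is about 11.8. With an assumed 150 or 267 DirectCAM completers, the implied SD is about 14.3 or 15.2.

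**Illustration of size.** The standard error follows from the design targets without an SD:

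SE = 4/(1.645 + 0.842) = 1.61 MFIS points.

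Take the margin as 4 points in the unfavourable direction, a shift of b points (assumed), and z = 1.960 for a two-sided 95% limit or 1.645 for one-sided 0.05.

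- False non-inferiority when the true difference is at the margin and b favours rDirectCAM: Φ(b/SE - z). For b = 1 and z = 1.960: Φ(0.622 - 1.960) = Φ(-1.338) = 0.090.
- Power when the true difference is 0 and b goes against rDirectCAM: Φ((4 - b)/SE - z). For b = 1 and z = 1.960: Φ(1.865 - 1.960) = Φ(-0.095) = 0.462.

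| Shift b | False non-inferiority, two-sided 95% limit | False non-inferiority, one-sided 0.05 | Power, two-sided 95% limit | Power, one-sided 0.05 |
|---|---|---|---|---|
| 0 | 2.5% | 5% | 70% | 80% |
| 1 | 9% | 15% | 46% | 59% |
| 2 | 24% | 34% | 24% | 34% |
| 4 | 70% | 80% | 2.5% | 5% |

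Both rules are shown because the sizing used one-sided 0.05, while the Enhancement Study analysis compares a limit of a 95% interval, read here as two-sided, with the margin.

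**The case against.** The strongest reply is that the limitation is disclosed and was hardly avoidable. The design is called quasi-experimental, on-site delivery had been suspended, and no concurrent on-site arm could be had. The rDirectCAM participants also came from the same sign-up stream as the Main study. This is fair, and the design itself is not at fault. But quasi-experimental tells the reader that allocation was not random; it does not say that the comparator is non-concurrent. A shared source supports similarity in who was enrolled, not in when they were followed. The same section goes on to state unbiasedness.

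The sentence can also be read as describing a technique in general, with weights conditional on observed covariates. Even so, it omits the assumption that nothing unobserved matters, and the reader will apply it to this comparison.

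Four stronger readings are tempting and are not supported:

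- A reader might infer that the estimate is biased. Bias needs a non-zero effect of period or mode on the change from baseline, and the documents report none. A constant offset at both baseline and follow-up would cancel.
- A reader might infer that season lies wholly inside the contrast, as period does. It does not, since DirectCAM enrolled in every calendar month.
- A reader might infer that pandemic exposure was confined to rDirectCAM. The 25 interrupted DirectCAM participants and some late follow-up visits contradict this. They do not restore overlap in enrolment date, and they raise a further question: how the 25 are labelled and handled in this comparison.
- A reader might take the Main-study post-COVID term as a measure of the period shift. It coincides with the switch to remote collection, so it mixes period with mode. It also describes people with pre-pandemic baselines and pandemic follow-up, whereas rDirectCAM had both within the pandemic.

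**Conclusion.** The point holds in a limited form. Enrolment period is fully aliased with arm and assessment mode largely so, and IPTW on observed baseline covariates cannot balance either. The unconditional statement of asymptotic unbiasedness is therefore not justified; what can be said is that unbiasedness is not established and that weighting cannot secure it. Neither the post-COVID covariate, which belongs to the Main study, nor the sensitivity analyses named for the Enhancement study address period.

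The possible size is material: under either decision rule, a shift well inside the 4-point MFIS margin could decide the verdict in either direction. The tabulated rates rest on an assumed shift and on a planning standard error, not on the standard error that the weighted analysis would produce. They cover MFIS only, although the plan sets margins for seven outcomes.

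**What to change.** In the Enhancement Study part of Analytical and Statistical Approaches:

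1. State that the weighted estimate is asymptotically unbiased only under no unmeasured confounding, positivity, and no period or assessment-mode effect on change from baseline. Name DirectCAM a non-concurrent comparator.
2. List the propensity covariates and add calendar month or season of baseline.
3. State how the 25 DirectCAM participants offered remote delivery are handled, and add a sensitivity analysis that excludes them.
4. For each outcome, report the period or mode shift that would reverse the non-inferiority verdict, which is the distance from the relevant confidence limit to the margin. Present this as a sensitivity analysis and word the conclusion to match.

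The verdict should not be made to depend on the Main-study post-COVID shift. If that shift is shown, label it as context that mixes period with collection mode.

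The cost is a few sentences, one more propensity covariate, one re-run without the 25, and one table, all from data already held. The downside is slightly more variable weights and a more guarded conclusion.
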